 - Assessment of adverse events

	
Post-Tc 99m Tilmanocept Injection Procedures and Follow-Up Visit (Visit 3):
 
 • 18-20 Hours Post Injection: 
 ○ Whole body planar imaging ○ PK blood sampling ○ Vital Signs ○ ECG ○ Physical Exam, including body weight ○ Clinical labs and urinalysis ○ Concomitant medication review ○ Assessment of Adverse Events 	

Planned study dates
	
Start of study recruitment / August 2016
	
End of Recruitment/July 2018 End of Study/September 2018

Planned number of study centers
	
Approximately 1-3 centers in the United States
	

Number of subjects
	
Up to 48 evaluable subjects may be enrolled. The dose escalation portion of this study is a modified 3+3 design with no dose de-escalation. The sequential cohort enrollment characteristics of this design do not allow a fixed computation of sample size. The parameters of the design that can be calculated are shown in Table 4. Based on an assumed vector of probabilities of no subjects experiencing pharmacologic activity or an Adverse Drug Reaction (ADR) in each dose group, the average sample size of the dose escalation phase of the study is n=26.3 patients and the probability that dose group 7 will be selected as the MTD (maximum tolerated dose) is 0.152.
	

Primary endpoint
	
Proportion of subjects not experiencing pharmacologic activity or ADR in each dose group.
	

Secondary endpoints
	
The secondary endpoints for this study are:
 
 • Per subject localization rate of Tc 99m tilmanocept by SPECT imaging • Per joint location clinically RA-identified joint localization rate of Tc 99m tilmanocept by SPECT imaging • Concordance of Tc 99m localization with anatomical areas of active RA defined by clinical symptomology. • Localization intensity for each clinically RA-defined joint (as determined by quantitative SPECT gamma counts) 	

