5.3 Treatment Assignment

In this open-label, non-randomized, multicenter, dose-escalation safety study all subjects will receive IV administration at one of 3 tilmanocept mass doses: 50 µg, 200 µg, or 400 µg. Within each mass dose group, subjects will receive tilmanocept labeled to one of 3 radiolabel Tc 99m doses: 1 mCi, 5 mCi, or 10 mCi.

Group 1 will be the starting dose group. Three subjects will be enrolled into Group 1. If none of the 3 subjects experiences pharmacologic activity or an ADR, 3 subjects will be enrolled in Group 2. However, if one of the first three subjects experiences a pharmacologic activity or an ADR, three more subjects will be treated at the same dose level. If 2 out of 3 or 3 out of 6 subjects experiences a pharmacologic activity or an ADR in Group 1 the MTD cannot be determined. If no additional pharmacologic activity or ADRs are observed in the expanded group, the dose escalation will continue. If one additional pharmacologic activity or ADR is observed, the current dose will be deemed the maximum tolerated dose (MTD). If more than one additional pharmacologic activity or ADR is observed in the expanded group, the previous dose will be deemed the MTD. Dose escalation will continue until the MTD is found or until Group 9 is reached with only one ADR or without any ADRs. If no ADRs are experienced from Groups 1-9, then the MTD will be highest tilmanocept mass dose radiolabeled at the highest level (400 µg/10 mCi).

Group 10 will consist of 6 HC subjects and Group 11 will consist of 6 subjects with active RA. Subjects enrolled in Groups 10 and 11 will be dosed at the dose level that is established as the MTD from Groups 1 through 9. The maximum tolerated dose is defined as the dose below where >33% of subjects experienced an ADR.

NOTE: Adverse Drug Reaction

An Adverse drug reaction (ADR) includes all noxious and unintended responses to a medicinal product related to any dose or dose regimen. The phrase “responses to a medicinal product” means that a casual relationship between a medicinal product and an adverse event is at least a reasonable possibility, i.e. the relationship cannot be ruled out.

In this multi-center trial, doses will be serially assigned in an open label fashion in accordance with [Table 1](#). Investigators who have identified a subject for participation will receive the dose assignment from the sponsor and request that dose from the supporting Cardinal Health pharmacy.

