9 STATISTICAL METHODS

The study is a prospective, open-label, multicenter, dose escalation, and safety with PK and dosimetry study of injected Tc 99m tilmanocept in the detection of and assessment of localization to skeletal joints in subjects with and without active RA by SPECT and SPECT/CT imaging. The dose escalation portion of the study is a modified 3+3 design with no dose de-escalation as described in [Chevret \(2006\)](#). The statistical objective of the study is to determine the maximum tolerated dose (MTD) of Tc 99m tilmanocept and to compare the capabilities of Tc99m tilmanocept between subjects with and without RA.

A study center is defined as a treatment administration site or group of treatment administration sites under the control and supervision the same Primary Investigator.

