9.2 Safety Variables

The primary variable for this study is whether a subject observes any pharmacologic activity or an ADR during their enrollment in the trial. This is a safety endpoint. The pharmacologic activity or ADR must be observed after the dose of Tc99m tilmanocept is administered.

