9.4 Sample Size Justification

The dose escalation portion of this study is a modified 3+3 design with no dose de-escalation. The sequential cohort enrollment characteristics of this design do not allow a fixed computation of sample size. The parameters of the design that can be calculated are shown in [Table 4](#). Based on an assumed vector of probabilities of any pharmacologic activity or an ADR for a subject, the probability of each dose being the MTD is shown in the table. The average sample size of the dose escalation phase of the study is $n=26.3$ patients for the assumed vector of probabilities of any pharmacologic activity or an ADR.

Table 4. Design Characteristics for the Study Design

Dose Group	1	2	3	4	5	6	7	8	9	Total
Assumed Probability of any pharmacologic activity or a ADR for a subject	.01	.02	.05	.08	.10	.13	.16	.19	.22	---
Probability of the Dose Being the MTD	.002	.012	.039	.071	.103	.136	.152	.148	.065	---
Average Sample Size for Each Dose and Total	3.1	3.2	3.4	3.5	3.3	3.2	2.8	2.2	1.6	26.3

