9.5.4 Analysis of RPK and Dosimetry Variables

The RPK variables for Groups 10 and 11 are the whole blood and urine radioactivity levels per time point. The radioactivity in whole blood will be measured directly using the blood samples. The radioactivity of urine will be obtained from counts of the bladder wall obtained from radiation dosimetry. RPK parameters will be estimated for each subject using noncompartmental models. Summary statistics (n, mean, std, CV, geometric mean) will be computed for each RPK parameter across all subjects by Group (10, 11).

For dosimetry data, for each dosimetry parameter, summary statistics (n, mean, std, and a one standard deviation width confidence interval) will be computed by organ type and overall across all subjects by Group (10, 11). Analysis of Safety Variables

The number and percentage of subjects with any pharmacologic activity or ADRs will be tabulated by dose group and overall.

All adverse events (AEs) will be observed for each subject from the time of signing of informed consent until exit from the study. A treatment emergent adverse event is defined as an adverse event whose start date is on or after the procedure date. If the procedure date and/or the AE start date are missing, the AE will be considered treatment emergent.

Prior to analysis, all adverse events (AEs) will be coded using the MedDRA coding dictionary. Based on these coded terms, treatment emergent AEs will be summarized by dose group and overall as follows:

- by system organ class and preferred terms
- by system organ class and preferred terms and relation to study drug
- by system organ class and preferred terms and severity

Observed and change from baseline vital sign parameters, ECG parameters and hematology, clinical chemistry and urinalysis parameters will be summarized using descriptive statistics (mean, median, standard deviation, minimum, maximum and range) at each time point by dose group and overall.

Other safety analyses will be described in the Statistical Analysis Plan (SAP) for the study.

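### With no ADRs in Groups 1-9, section 5.3 names 400 µg/10 mCi the MTD although its own definition is not met; the accurate label is MTD not reached, highest dose tested

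*Combined protocol and SAP*

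**What the plan says.** Section 9 of the protocol sets the aim: "The statistical objective of the study is to determine the maximum tolerated dose (MTD) of Tc 99m tilmanocept", together with a comparison between subjects with and without RA.

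Section 5.3 (Treatment Assignment) contains three statements that bear on the zero-ADR case:

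- The definition: "The maximum tolerated dose is defined as the dose below where >33% of subjects experienced an ADR".
- The end of escalation: "Dose escalation will continue until the MTD is found or until Group 9 is reached with only one ADR or without any ADRs".
- The fallback: "If no ADRs are experienced from Groups 1-9, then the MTD will be highest tilmanocept mass dose radiolabeled at the highest level", given in parentheses as 400 µg/10 mCi. That is the Group 3 cell of Table 1.

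Section 5.3 does say that the MTD cannot be determined when Group 1 has too many events. It has no matching outcome at the top of the range.

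Section 9.4 gives an assumed event probability for each group, and "the probability of each dose being the MTD is shown in the table" (Table 4). The synopsis highlights one entry: "the probability that dose group 7 will be selected as the MTD (maximum tolerated dose) is 0.152".

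The primary variable in section 9.2 is a composite: "whether a subject observes any pharmacologic activity or an ADR during their enrollment in the trial". The planned summary, under section 9.5.4, is: "The number and percentage of subjects with any pharmacologic activity or ADRs will be tabulated by dose group and overall". The same section leaves other safety analyses to a SAP whose text is not among the material supplied.

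**The concern.** An MTD is a statement about where tolerability runs out. If escalation finishes without an ADR, the data say only that no limit was found up to the highest dose given. Section 5.3 would have the report state an MTD anyway, in conflict with the definition in the same section.

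The stake is how a stated statistical objective is reported. A later reader, or a later protocol citing this one, could take 400 µg/10 mCi as a ceiling established by data when it is only the top of the planned range. The plan's text would place a bare 0% from three subjects next to that label.

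**Working it through.** **1. Definition against fallback.** With no ADRs, the ADR proportion is 0% in every group. No group exceeds 33%, so no dose lies below such a group, and the definition selects nothing. The fallback selects 400 µg/10 mCi. The sentence before the fallback lists finding the MTD and reaching Group 9 with at most one ADR as alternatives, which fits an outcome in which no MTD was found.

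**2. Reproducing Table 4.** The inputs are Table 4's assumed probabilities, p = .01, .02, .05, .08, .10, .13, .16, .19, .22 for Groups 1-9, with q = 1 − p. From section 5.3, with cohorts of three:

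- Escalate (0/3, or 1/3 then 0/3): E = q³ + 3pq²·q³
- Current dose is the MTD (1/3 then 1/3): C = (3pq²)²
- Previous dose is the MTD (two or more additional events): D = 1 − E − C. The same consequence is assumed for two or more events in the first three.

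P(reach group g) is the product of E over the earlier groups. P(MTD = g) = P(reach g)·C(g) + P(reach g+1)·D(g+1).

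| Group | P(reach) | E | P(MTD), computed | P(MTD), Table 4 |
|---|---|---|---|---|
| 1 | 1.0000 | 0.9988 | .0021 | .002 |
| 2 | 0.9988 | 0.9954 | .0115 | .012 |
| 3 | 0.9943 | 0.9734 | .0394 | .039 |
| 4 | 0.9679 | 0.9369 | .0715 | .071 |
| 5 | 0.9068 | 0.9061 | .1028 | .103 |
| 6 | 0.8217 | 0.8529 | .1360 | .136 |
| 7 | 0.7008 | 0.7934 | .1526 | .152 |
| 8 | 0.5560 | 0.7302 | .1483 | .148 |
| 9 | 0.4060 | 0.6651 | .0655 | .065 |

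Every entry agrees within 0.001. The average sample size comes out at 26.5 against the printed 26.3, a small difference that does not affect this point.

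**3. Where the rest of the probability goes.** The printed MTD row sums to 0.728, leaving 0.272. The computed row sums to 0.7297. P(pass Group 9) = 0.4060 × 0.6651 = 0.2700, and P(failure at Group 1, MTD undeterminable) = 0.0003. The total is 0.7297 + 0.2700 + 0.0003 = 1.000. Table 4 therefore treats completing the escalation as an outcome with no MTD.

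**4. How much of the 0.270 is the zero-ADR case.** Table 4's rates are for pharmacologic activity or an ADR, while the fallback counts ADRs only. If every event is an ADR, the case requires 27 event-free subjects: the product of q³ over the nine groups is 0.044. If no event is an ADR, it is the whole 0.270. The documents give no split, so at these rates only the range 0.044 to 0.270 can be stated.

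**5. What the data at that dose could show.** Table 1 plans three subjects in Group 3. If they have no event of either kind, the exact one-sided 95% upper bound is 1 − 0.05^(1/3) = 0.632. A true rate of one third would give 0/3 with probability (2/3)³ = 0.296. Over all nine groups with no event, 0/27 gives 1 − 0.05^(1/27) = 0.105.

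**The case against.** The strongest defence is that this is an explicit, prespecified convention: one sentence says when to stop and the next says which dose to carry forward. That stands as far as dosing goes, because the dose for Groups 10-11 in this case is clear. It does not make the label satisfy the definition in the same section.

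A second defence reads the definition loosely, as the highest dose with no more than 33% ADRs. Section 5.3 itself departs from the strict wording: at 2/6, which is 33.3%, it names the current dose. So the strict sentence is not the only operating rule. But at 2/6 a limit has at least been met in the data, whereas at 0% throughout nothing has been located. The loose reading also does not explain why Table 4 leaves 0.270 credited to no dose.

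Third, the primary objective is safety and tolerability, and the proportions would be reported correctly whatever the label. That is right, and it keeps the point small.

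Some stronger inferences are tempting, and the documents do not support them:

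- *Table 4 is wrong because its row does not sum to 1.* It reproduces; the remainder is passing Group 9.
- *The fallback makes Group 3 a more likely MTD than the highlighted Group 7.* That depends on the share of events that are ADRs, which the documents do not give.
- *The trial plans no confidence limits at all.* Section 9.5.4 defers other safety analyses to a SAP that is not available here.

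**Conclusion.** The point holds for the label, and it is minor. In the zero-ADR case section 5.3 declares an MTD that its own definition does not identify and that Table 4 does not count. The conflict is textual and rests on no assumed rate. The supporting figure of 0.270 rests on Table 4's assumed probabilities and independent subjects; it is the chance of passing Group 9 by any route, and the zero-ADR case is only part of it. The 63% bound assumes that Group 3 also has no pharmacologic activity and so stays at three subjects.

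A reader might infer that Groups 10-11 could receive an unintended dose. In this case they could not: nobody is dosed differently. Passing Group 9 with an ADR is a separate branch, to which this conclusion does not extend.

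**What to change.** In section 5.3, for the zero-ADR case only, replace the clause that names an MTD with: *the MTD was not reached; 400 µg/10 mCi is the highest dose tested and will be the dose for Groups 10-11*. The phrase *highest dose tested* is correct because that cell is highest in both mass and activity, although it is Group 3 and not the last group.

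Wherever Groups 10-11 are tied to the MTD (synopsis, section 3.2, the note to Table 1, section 5.3), add: *or, if no ADRs occurred in Groups 1-9, the highest dose tested (400 µg/10 mCi)*. This wording is deliberately confined to the zero-ADR case. The branch that passes Group 9 with an ADR needs its own rule from the sponsor.

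Optionally, unless the SAP already does so, show exact Clopper-Pearson limits beside the primary proportion by dose group and overall. They describe precision and are not a test of each group against 33%, since even 0/3 has an upper bound of 63%.

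The cost is a few words and, if the option is taken, a column in a planned table from data already collected. Enrolment and dosing do not change. The only drawback for the sponsor is a less favourable headline.

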5.2 Investigational Product Dosage and Administration

Subjects will receive the administration of Tc 99m tilmanocept through an intravenous (IV) route of administration. For the 50 and 200 µg doses a single syringe will be used and injected as a slow push into the Y-port. For the 400 µg dose 2 syringes will be used and injected sequentially as a slow push into the Y-port. At the completion of the injection(s), a 10 cc sterile normal saline flush will be administered. Injection volume will be between 0.5 - 4.0 ml in sterile normal saline based on the mass dose group assignment. The preferred site of IV placement will be the left or right antecubital vein unless both elbows are primary sites for RA imaging, and then the site for IV placement will be between the elbow and the wrist.

Tc 99m tilmanocept will be received by subjects through IV administration at one of 3 mass doses: 50 µg, 200 µg, or 400 µg. Within each mass dose group, subjects will receive Tc 99m tilmanocept labeled to one of 3 radiolabel doses: 1 mCi, 5 mCi, or 10 mCi (see Table 1).

Table 1. Dose Escalation Matrix

	Tilmanocept Mass Dose		
Specific Radioactivity Tc 99m	50 µg	200 µg	400 µg
10 mCi	Group 1 n = 3 RA	Group 2 n = 3 RA	Group 3 n = 3 RA
5 mCi	Group 4 n = 3 RA	Group 5 n = 3 RA	Group 6 n = 3 RA
1 mCi	Group 7 n = 3 RA	Group 8 n = 3 RA	Group 9 n = 3 RA

***Group 10 will consist of 6 HC (3 female subjects and 3 male subjects) and Group 11 will consist of 6 subjects (3 female subjects and 3 male subjects) with active RA. Subjects in Groups 10 and 11 will be enrolled in parallel and will be dosed at the MTDs determined from Groups 1-9.**

The final administered dose for groups will be ± 20% of the tilmanocept mass dose and radiolabel mCi dose assignment.

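### Section 5.3's closing MTD definition does not match its own escalation rule or Table 4, and no MTD is named when the ladder is completed with a tolerated ADR

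*Combined protocol and SAP*

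**What the plan says.** Section 5.3 contains three rules about the MTD.

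- **Escalation rule.** The event is pharmacologic activity or an ADR. With 0 of 3, escalate. With 1 of 3, add three subjects. With no further event, escalate. At 2 of 6, "If one additional pharmacologic activity or ADR is observed, the current dose will be deemed the maximum tolerated dose (MTD"). At 3 or more of 6, "If more than one additional pharmacologic activity or ADR is observed in the expanded group, the previous dose will be deemed the MTD". For the first group, 2 out of 3 or "3 out of 6 subjects experiences a pharmacologic activity or an ADR in Group 1 the MTD cannot be determined".
- **End of the ladder.** Escalation runs until an MTD is found or "until Group 9 is reached with only one ADR or without any ADRs". The sentence after it reads "If no ADRs are experienced from Groups 1-9, then the MTD will be highest tilmanocept mass dose", at the highest activity (400 µg/10 mCi, which is Group 3).
- **Closing definition.** "The maximum tolerated dose is defined as the dose below where >33% of subjects experienced an ADR".

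The Table 1 footnote in Section 5.2 says that Groups 10 and 11 "will be dosed at the MTDs determined from Groups 1-9". Section 9.2 gives the same event as the escalation rule: "The primary variable for this study is whether a subject observes any pharmacologic activity or an ADR during their enrollment in the trial". Table 4 in Section 9.4 also assumes probabilities for that combined event.

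**The concern.** The sentence labelled as the definition differs from the operative rule in two ways. It drops pharmacologic activity from the event, and its threshold does not lead to the rule's decision at 2 of 6. The end-of-ladder sentences also count ADRs only, and they leave a case open. Completion with an ADR is foreseen, but a dose is named only when there were none.

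The MTD sets the dose for all 12 subjects in Groups 10 and 11, and so for all PK and dosimetry results. After a completed ladder with a tolerated ADR, a reader could choose Group 9 (400 µg/1 mCi, the last step) or Group 3 (400 µg/10 mCi, the dose named for the event-free case). These have the same mass and a tenfold difference in activity. In an open-label trial that choice would be made after the data are seen.

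**Working it through.** **Inputs.** The event rates for Groups 1-9 are those of Table 4: .01, .02, .05, .08, .10, .13, .16, .19, .22. The decision rule is that of Section 5.3. One assumption is needed: the outcome at 2 or more of the first 3 is written only for Group 1, and I send it to the previous group in Groups 2-9.

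**Formulas, per group with rate p.** P0 = (1-p)³; P1 = 3p(1-p)²; P2+ = 1 - P0 - P1.

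- Escalate: P0 + P1·P0
- 2 of 6, current dose is the MTD: P1²
- Exceeded, previous dose is the MTD: P2+ + P1·P2+

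The probability of reaching a group is the product of the escalation probabilities before it.

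**Step 1. Reproduce Table 4.**

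| Group | 1 | 2 | 3 | 4 | 5 | 6 | 7 | 8 | 9 |
|---|---|---|---|---|---|---|---|---|---|
| Table 4 | .002 | .012 | .039 | .071 | .103 | .136 | .152 | .148 | .065 |
| 2/6 keeps current dose | .0021 | .0115 | .0394 | .0715 | .1028 | .1360 | .1526 | .1483 | .0655 |
| 2/6 goes to previous dose | .005 | .026 | .061 | .085 | .121 | .145 | .150 | .136 | 0 |

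The operative rule reproduces the row within .001. The average sample size is 26.5, against 26.3 stated. Sending 2 of 6 to the previous dose does not reproduce the row. Nor does escalating through 2 of 6, which gives .001 to .121 for Groups 1-8, 0 for Group 9 and an average of 30.2 subjects. Table 4 was therefore built on the operative rule, and the closing sentence is the outlier.

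**Step 2. The closing sentence at 2 of 6.** 2/6 = 33.3% exceeds 33%. Taken literally, the MTD is the dose below, and in Group 1 there is none, although Group 1 fails only at 2 of 3 or 3 of 6. If 33% stands for one third, 2/6 does not exceed it, and 3/6 and 2/3 do, which fits the Group 1 boundary. But escalation has then stopped without any group above one third, so the sentence names no dose. On either reading the event is ADRs only.

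The probability of stopping at 2 of 6 is the sum of reach × P1²: .0009 + .0033 + .0182 + .0399 + .0535 + .0716 + .0804 + .0778 + .0655 = .411.

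**Step 3. The end of the ladder.**

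- Completed (product of the nine escalation probabilities): .2700
- No event in 27 subjects (product of the nine P0): .0438
- Completed with at least one tolerated event: .2700 - .0438 = .226, which is 84% of completions

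The >33% sentence cannot fill this gap, because every group then has 0 of 3 or 1 of 6. As a check on the total: .7297 (stops that name an MTD) + .2700 + .0003 (Group 1 exceeded) = 1.

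With one constant rate in all nine groups (my assumption, to show the range):

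| Rate | Completed | No event | Gap |
|---|---|---|---|
| 0.12% | .9998 | .9681 | .032 |
| 1% | .9895 | .7623 | .227 |
| 2% | .9596 | .5796 | .380 |
| 5% | .7849 | .2503 | .534 |

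**Step 4. The order of Table 1.** Group 4 (50 µg/5 mCi) follows Group 3 (400 µg/10 mCi), and Group 7 (50 µg/1 mCi) follows Group 6 (400 µg/5 mCi). When Group 4 or Group 7 is exceeded, the previous dose is higher in both mass and activity. The probability is .0212 + .0644 = .086.

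**The case against.** The strongest reply is that Section 5.3 already gives an explicit instruction at 2 of 6, that Table 4 reproduces under it, and that 33% is naturally read as one third. On that view the closing sentence is only a loose summary. Most of this stands. The intent at 2 of 6 can be recovered, and neither the escalation rule nor Table 4 is wrong. What survives is that the sentence presented as the definition counts a different event and does not return the rule's answer.

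A reader might take the 0.411 as the chance that the trial picks the wrong dose. The documents do not support that. It is the probability of stopping at 2 of 6. It would equal disagreement between rule and definition only under the literal 33.0% reading with every event an ADR. The documents do not split ADRs from pharmacologic activity, so the actual rate cannot be computed.

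A reader might also infer that the end-of-ladder gap is large whatever the event rate. It is not. Section 1.3.5 reports post-marketing adverse events in fewer than 0.12% of subjects, and at that rate the gap is about 0.03. That figure comes from other routes of administration (Section 8.6.1.4), so it is illustrative, but it shows how far the bound moves.

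The reply does not reach the missing sentence itself. No section names an MTD for a ladder completed with a tolerated ADR, at any event rate.

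**Conclusion.** The concern holds as an inconsistency and an omission in Section 5.3, and it should be fixed. The closing definition conflicts with the operative rule on the event, and on the decision at 2 of 6 it either contradicts the rule or is silent. The end-of-ladder gap is the more consequential part: up to 0.226 of trials under Table 4's rates would have no named dose for Groups 10 and 11.

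That figure rests on Table 4's assumed rates, on independent subjects, on sending 2 of 3 to the previous group, and on every event being an ADR. If some events are pharmacologic activity only, the gap is smaller. The inconsistency and the missing sentence depend on none of these assumptions.

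**What to change.** 1. Replace the closing sentence of Section 5.3 with the operative rule for every group, counting subjects with pharmacologic activity or an ADR. With 0 of 3 or 1 of 6, escalate. With exactly 2 of 6 (one in each set of three), stop; the current dose is the MTD. With 2 or more of the first 3, or 3 or more of 6, the dose is exceeded; in Group 1 the MTD cannot be determined.
2. Change the condition of the end-of-ladder sentence to: *If no group stops escalation (each of Groups 1-9 has 0 of 3 or 1 of 6 subjects with an event)*. Keep the stated 400 µg/10 mCi assignment.
3. Add to Table 4 the 0.270 probability of completing the ladder, and note that it goes to 400 µg/10 mCi. Group 3's total becomes .039 + .270 = .309, and the existing row then covers stops by events only. Adjust the describing text in Section 9.4 and the synopsis, which quotes Group 7 at 0.152.
4. Do not fix the MTD as the previous group where that group is higher in both mass and activity. State that Groups 10 and 11 will not receive a dose at or above an exceeded dose in both. Every group before Group 4 has at least 50 µg and 10 mCi, and every group before Group 7 at least 50 µg and 5 mCi. No tested dose therefore qualifies after either is exceeded, and the text should say how the dose is then decided. Footnote Table 4 that .0212 of Group 3's probability and .0644 of Group 6's arise this way. If these outcomes are instead counted as no MTD, Group 3 becomes .018 + .270 = .288 and Group 6 .072.

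The cost is wording in Section 5.3, one line and a footnote in Table 4, and the text that describes it. No subjects or procedures are added.
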